9.5.2. Treated Infections

A treated infection is any infection that requires antimicrobial therapy by any route of administration or any surgical intervention (eg, incision and drainage). A subject who experiences a serious infection must be discontinued from the study. This information must be noted in the eCRF.

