After randomization, subjects will be required to maintain a stable dose of CSs during the withdrawal phase. Subjects who flare at any time during the randomized withdrawal phase, or who experience 24 consecutive weeks of inactive disease as assessed using JIA ACR (clinical remission) (Wallace 2011)¹⁶, will complete their participation in the study. An end-of-study visit should be performed. Subjects who discontinue Investigational Product in the double-blind phase of the study due to any reason will be counted as having an sJIA flare in the primary analysis for the primary endpoint of the study and will contribute to the requisite number of subjects with flare for the study to be considered complete. Subjects who achieve clinical remission are completers of the study and will not be counted as having an sJIA flare in the primary analysis. Upon notification by the Sponsor, an end-of-study visit should be scheduled for all remaining subjects in the study in accordance with [Section 6.8](#).

All subjects participating in this study, including those discontinued from the study, will have the option, if eligible, of enrolling in the tofacitinib long-term extension study (A3921145). The Sponsor’s intent is to make tofacitinib available to pediatric subjects through Study A3921145.

Subjects who discontinue Investigational Product in the double-blind phase for reasons other than sJIA flare, and who do not enter A3921145 are required to continue in the study and perform all scheduled visits until Week 52 after randomization or until the study concludes, whichever comes first. Such subjects should transition to standard-of-care treatment in accordance with local treatment guidelines.

[figure not shown]
3.4. Sequential Evaluation of Tofacitinib 5 mg BID Dose in Cohorts in Part 1

Dosing will not exceed 5 mg BID, which is the approved dose for adult RA patients.

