6.7.1. Discontinuation from Investigational Product during Randomized Withdrawal Phase

Subjects who discontinue Investigational Product in the double-blind phase, for reasons other than sJIA flare, and who do not rollover to A3921145 LTE study, should continue with the regular scheduled visits every 4 weeks up to and including Week 52. All required procedures and assessments listed above should be performed with the exception of IP dispensing and compliance. Subjects should receive standard-of-care treatment as per local guidelines. There are no protocol restrictions on the use of DMARDs and other disallowed agents, detailed in Appendix 1, for subjects receiving standard of care treatment.

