6.8. End of Study or Early Termination Visit

Each subject's participation in the study will end once the subject experiences a first sJIA flare in the double-blind phase or 24 consecutive weeks of inactive disease (clinical remission). An end-of-study visit should be performed.

Subjects who are not able to maintain an Adapted JIA ACR 30 response for 4 weeks in the open-label phase, or who have fever due to sJIA lasting more than 2 consecutive days in Part 1, or who fail CS tapering more than twice in Part 2 of the open-label phase will need to be discontinued from the study.

Subjects will have the option, if eligible (based on inclusion and exclusion criteria), of enrolling in the tofacitinib JIA long-term extension study (A3921145) after withdrawal or completion of this study.

- Subjects who discontinue investigational product in the double-blind phase and who do not enter A3921145 will be required to continue in the study and perform all scheduled visits until Week 52 after randomization or until the study concludes, whichever comes first. Such subjects should transition to standard-of care treatment in accordance with local guidelines.
- Subjects who discontinue in the Open-Label Phase and do not enter A3921145 will be required to return for a follow up visit 28 days after the last dose of study treatment.

The study will be completed once the requisite number of subjects have reported flare in the double-blind withdrawal phase (refer to [Section 11](#)). At that time and upon notification by the Sponsor, the investigator will be required to schedule an end-of-study visit for all remaining active subjects.

If a subject discontinues from the study at a regularly scheduled study visit, all assessments and procedures for that visit should be completed. In addition, a Tanner stage assessment should be done as part of the study termination. If a subject discontinues outside of a regularly scheduled visit, an Early Termination visit should be scheduled as soon as possible. The procedures and assessments listed below will be performed at the End of Study or Early Termination visit.

Subjects should be instructed to fast, if possible, for lipid panel testing.

- Review concomitant medications. Refer to [Section 5.8](#).
- Complete physical exam, including skin examination for chickenpox or shingles. **Country specific amendment for EU sites (including UK):** a full skin cancer examination must be performed as part of the complete physical examination.

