7. DISCONTINUATION OF STUDY INTERVENTION AND PARTICIPANT DISCONTINUATION/WITHDRAWAL

7.1. Discontinuation of Study Intervention

It may be necessary for a participant to permanently discontinue study intervention. Reasons for permanent discontinuation of study intervention include the following;

- Insufficient clinical response
- Adverse events
- Medication error without associated adverse event
- Subject died
- Protocol violation
- Lost to-follow up
- Does not meet entrance criteria
- No longer willing to participate in study
- Pregnancy
- Study terminated by sponsor

The criteria for discontinuation of investigational product in the open-label phase, (part 1 and part 2), are detailed in Section 3.2.

If study intervention is permanently discontinued during the double-blind phase, and the participant does not enter A3921145, the participant should remain in the study for follow-up to be evaluated for safety and efficacy endpoints. See the SCHEDULE OF ACTIVITIES and [Section 6](#) for data to be collected at the time of discontinuation of study intervention and follow-up visit requirements.

Subjects will have the option, if eligible (based on inclusion and exclusion criteria), of enrolling in the tofacitinib JIA long term extension study (A3921145) after completion of this study.

In the event of discontinuation of study intervention, it must be documented on the appropriate CRF/in the medical records whether the participant is discontinuing further receipt of study intervention or also from study procedures, posttreatment study follow-up and/or future collection of additional information.

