8.3.2. Discontinuation of Study Drug Criteria

Study drug will be discontinued in the event of any of the following:

- Serious infections defined as any infection (viral, bacterial, or fungal) requiring parenteral antimicrobial therapy or hospitalization for treatment, or meeting other criteria that require the infection to be classified as a serious adverse event (see [Section 9.5.1](#));
- Opportunistic infection judged significant by investigator;
- Two sequential absolute neutrophil counts $<0.5 \times 10^9/L (<500/\text{mm}^3)$;
- Two sequential hemoglobin values $<8.0 \text{ g/dL (80 g/L)}$ or decreases of $>30\%$ from baseline value;
- Two sequential absolute lymphocyte counts $<0.5 \times 10^9/L (<500/\text{mm}^3)$ by repeat testing;
- Two sequential platelet counts $<75 \times 10^9/L (<75,000/\text{mm}^3)$;
- Two sequential AST or ALT elevations >3 times ULN with a total bilirubin value ≥ 2 times the upper limit of normal;^a
- Two sequential AST or ALT elevations >3 times ULN with an elevated INR;^a
- Two sequential AST or ALT elevations >3 times ULN accompanied by signs or symptoms consistent with hepatic injury;^a
- Two sequential AST or ALT elevations >5 times ULN, regardless of total bilirubin or accompanying symptoms;
 - The subject must return to the study site for prompt retesting and include the following: albumin, creatine kinase (CK), total bilirubin, direct and indirect bilirubin, GGT, PT/INR, and alkaline phosphatase. Additional investigations include a detailed history, occupational exposure, sexual history, travel history, history of contact with a jaundiced subject, surgery, blood transfusion, history of liver or allergic disease, work exposure, history of ethanol, recreational drug and dietary supplement consumption. Testing for acute hepatitis A, B or C infection and biliary tract imaging may be considered.

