9.5.1. Serious Infections

A serious infection is any infection that requires hospitalization for treatment or requires parenteral antimicrobial therapy or meets other criteria that require it to be classified as a serious adverse event. A subject who experiences a serious infection must be discontinued from Investigational Product. This infection must be reported as a serious adverse event and should be listed as the reason for discontinuation of study drug in the CRF. Appropriate laboratory investigations, including but not limited to cultures should be performed to establish the etiology of any serious infection. All adverse events, including serious adverse events, must be reported as described in [Section 9.1](#) on Adverse Event Reporting.

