Appendix 7. Guidelines For Safety Monitoring And Discontinuations

The following laboratory abnormalities require prompt re-testing, ideally within 3-5 days:

- Lymphocyte counts <500 lymphocytes/mm³.
- Neutrophil counts <1000 neutrophils/mm³.
- Platelet counts <100,000 platelets/mm³.
- Any single hemoglobin value <8.0 g/dL.
- Any single hemoglobin value that is ≥ 2 gm/dL below the baseline.
- Any single AST and/or ALT elevation >3 times the upper limit of normal, regardless of the total Bilirubin (repeat laboratory testing must include CK, Total Bilirubin, Direct and Indirect Bilirubin, GGT, INR and alkaline phosphatase).
- Any single serum creatinine increase $>50\%$ over the average of screening (most recent value prior to baseline) and baseline values OR an absolute increase in serum creatinine ≥ 0.5 mg/dL (≥ 44.2 umol/L) AND any single CrCl decrease of $>30\%$ over the average of screening (most recent value prior to baseline) and baseline values.
- Increased lipid parameters (total cholesterol, LDL cholesterol, HDL cholesterol, triglycerides) should be monitored and treated according to local guidance (eg, diet and behavior modification, statin therapy).

Temporary Withholding and discontinuation of Investigational Product related to Venous Thromboembolism:

- Per Amendment 3, for subjects with suspected venous thromboembolism, investigational product treatment should be temporarily withheld while the subject is evaluated. If venous thromboembolism is confirmed, discontinue investigational product. Refer to [Section 8.2.14](#).

Investigational Product will be discontinued for:

- Serious infections (those requiring parenteral antimicrobial therapy or hospitalization), and opportunistic infections;
- Malignancies, excluding adequately treated or excised basal cell or squamous cell carcinoma of the skin and cervical carcinoma in situ;
- Confirmed venous thromboembolism;
- Two sequential lymphocyte counts <500 lymphocytes/mm³;
- Two sequential neutrophil counts <500 neutrophils/mm³;

- Two sequential platelet counts <75,000 platelets/mm³;
- Two sequential hemoglobins <8.0 g/dL or a decrease of more than 30% from baseline value;
- Two sequential AST or ALT elevations >3 times the upper limit of normal with at least one Total Bilirubin value >2 times the upper limit of normal;
- Two sequential AST or ALT elevations >3 times the upper limit of normal with an abnormal INR;

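### Protocol 9.5.2 takes a subject with a serious infection out of the study, whereas the rest of the protocol stops product only and keeps double-blind non-rollover subjects in follow-up to Week 52 or study end

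*Protocol*

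**What the plan says.** Two adjacent sections of the protocol give different mandatory actions for one event.

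- Protocol 9.5.1, which defines serious infection: "A subject who experiences a serious infection must be discontinued from Investigational Product".
- Protocol 9.5.2, under the heading for treated infections: "A subject who experiences a serious infection must be discontinued from the study".

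Two other places list the same event as a reason to stop drug. Protocol 8.3.2 introduces its list with "Study drug will be discontinued in the event of any of the following", and serious infection is the first item. Appendix 7 lists, among the reasons for stopping Investigational Product, "Serious infections (those requiring parenteral antimicrobial therapy or hospitalization), and opportunistic infections".

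Four sections say what follows when product stops in the double-blind phase and the subject does not enter the extension study A3921145.

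- Section 3.3 (reasons other than flare): such subjects, "who do not enter A3921145 are required to continue in the study and perform all scheduled visits until Week 52 after randomization" or study end.
- Section 6.7.1 (reasons other than flare): they "should continue with the regular scheduled visits every 4 weeks up to and including Week 52".
- Section 6.8: they "will be required to continue in the study and perform all scheduled visits until Week 52 after randomization or until the study concludes".
- Section 7.1: "the participant should remain in the study for follow-up to be evaluated for safety and efficacy endpoints".

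Section 7.1 names adverse events among the reasons for stopping product. Section 7.2 gives reasons for leaving the study and names neither infection nor adverse events, although its list is not presented as exhaustive.

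**The concern.** Both 9.5.1 and 9.5.2 are worded as obligations, and no clause says which prevails. A site that opens 9.5.2 after a serious infection could end the subject's participation, while the SAP assumes that participation continues.

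Three analyses rely on data collected after product stops:

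- **Estimand 3** (SAP 2.3.2.2; secondary): treatment policy for change in the JIA core variables, using on- and off-product data to Week 52. Lost visits are left to the MMRM.
- **Estimand 5** (SAP 2.3.3; supplementary): treatment policy for time to flare. Under SAP 5.3.1.1 the subject is censored at the last available flare assessment, so the censoring comes early.
- **Estimand 6** (SAP 2.3.4; supplementary): treatment policy for adapted JIA ACR response. The estimand says that stopping product is not itself non-response, but SAP 5.3.2 sets remaining missing visits to non-response. An unnecessary study exit therefore brings back the rule that the estimand sets aside.

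Protocol 2.3.1 lists infection as a risk that may be associated with tofacitinib, so such losses could be related to treatment. The documents give no expected rate.

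**Working it through.** **Which sentence is out of line.** The texts sort as follows.

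| Place in protocol | Action for serious infection, or after stopping product |
|---|---|
| 9.5.2 | leave the study |
| 9.5.1, 8.3.2, Appendix 7 | stop product |
| 3.3, 6.7.1, 6.8, 7.1 | double-blind, not rolling over: stay in follow-up |
| 9.13 | describes withdrawal from product because of an SAE |

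By 9.5.1 a serious infection is reported as an SAE, so 9.13 covers it. The 9.5.2 sentence defines nothing; it restates the action for an event that 9.5.1 already handles, and restates it differently. Retention is the intended rule.

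**How much follow-up one subject could lose.** The plan states no figure for this, so there is none to reproduce. Assumptions:

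- visits every 4 weeks, so 52/4 = 13 to Week 52;
- product stops at Week *s*, with an early termination visit at Week *s*;
- the follow-up visit of Protocol 6.9 falls at about Week *s* + 4 (28 days after the last dose);
- no flare, and no study end, before Week 52.

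Let *L* be the week of the last flare assessment if the site follows 9.5.2. Protocol 6.9 assesses flare at the follow-up visit only for stops before Week 24, which gives *L* = *s* + 4 if *s* < 24 and *L* = *s* otherwise. The Schedule of Activities and SAP 6.1.2.1 carry no such limit, which gives *L* = *s* + 4 throughout. Then

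lost visits = (52 − *L*)/4; lost days = 364 − 7*L*.

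| Stop (*s*) | *L* | Lost visits of 13 | Lost days |
|---|---|---|---|
| 4 | 8 | (52 − 8)/4 = 11 (85%) | 364 − 56 = 308 |
| 12 | 16 | (52 − 16)/4 = 9 (69%) | 364 − 112 = 252 |
| 24 | 24 or 28 | 7 or 6 (54% or 46%) | 196 or 168 |
| 36 | 36 or 40 | 4 or 3 (31% or 23%) | 112 or 84 |

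These are maxima. Under Protocol 3.3 and 6.8, participation also ends at a first double-blind flare, so a retained subject who flares off drug has no later visits to lose. The planning median to flare on placebo is 236 days (Protocol 10.1.1), shorter than the 308- and 252-day figures, so an earlier flare is quite possible. The flare hazard on standard of care is not in the documents, so no expected loss can be given.

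**What one subject does to Estimand 6.** Protocol 10.1.1 plans 54 randomized 1:1, or 27 per arm. A lost subject who would have responded lowers that arm's rate by 1/27 = 3.7 percentage points at each lost visit; a non-responder changes nothing. This holds for any one missing responder, so it scales a subject and does not measure how often the defect bites.

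**Primary analysis.** Under SAP 2.3.1, stopping product for any reason other than clinical remission or study end is a flare on the day it stops. Later data are not used. The effect is 0 under either reading.

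**The case against.** The strongest reply is that this is a leftover wording slip and the intended rule is easy to recover. Retention is repeated across the protocol, the action for serious infection belongs to 9.5.1, and Section 7.1 makes sites record whether a subject is stopping product only or study procedures as well. The Amendment 7 entry in the change log also points to retention. All of this stands, and it is why the sentence can be called wrong instead of merely ambiguous. It does not make the sentence harmless, because a site is still told that it must do the opposite.

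Four stronger readings are tempting, and the documents do not support them.

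- *That 9.5.2 is wrong for every subject.* The retention rule covers the double-blind phase only. Open-label subjects who stop and do not roll over have just a follow-up visit 28 days after the last dose, so nothing is lost there. Subjects who enter A3921145 still contribute flares to Week 52 in Estimand 5.
- *That the visit counts are expected losses.* They are upper limits, for the reasons given in the working.
- *That follow-up of the infection itself is lost.* Protocol 9.2 continues it until the event resolves or stabilises, and active collection runs at least 28 days after the last dose, subject to consent. Only routine collection beyond that would be cut short.
- *That Section 8.2.6 (varicella or zoster), which also calls for study exit, is the same error.* The protocol prescribes study exit for other specific events too: confirmed pregnancy (8.2.10) and need for a disallowed DMARD (5.8.1.2, Appendix 1). Section 8.2.6 may be a deliberate exception.

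**Conclusion.** The inconsistency is real. For double-blind subjects who stop product because of a serious infection and do not enter A3921145, the 9.5.2 sentence contradicts the follow-up rule and is wrong as written. The cost is avoidable loss of planned off-drug data in one secondary and two supplementary estimands. It is bounded per subject by the visit counts above, which assume four-weekly visits and neither a flare nor study end before Week 52. The total effect cannot be sized, because the number of such infections is not given. A reader might infer that the primary result or its event count is at risk; it is not, since the subject counts as a flare either way. The case for acting is that the data are planned for, the randomized sample is small, and the correction costs almost nothing.

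**What to change.** In Protocol 9.5.2, change the object of the discontinuation from the study to Investigational Product, or delete the sentence, since 9.5.1 already covers the event. Add a reference to 6.7.1 and 7.1 for subjects in the double-blind phase.

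As a separate note, the sponsor should confirm whether study exit is intended for varicella or zoster in 8.2.6. If it is, a short statement of that exception in 7.1 would help.

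The cost is a few words and a cross-reference. Procedures, sample size and the primary analysis stay as they are.

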9.6. Abnormal Test Findings

The criteria for determining whether an abnormal objective test finding should be reported as an AE are as follows:

- Test result is associated with accompanying symptoms; and/or
- Test result requires additional diagnostic testing or medical/surgical intervention; and/or
- Test result leads to a change in study dosing or discontinuation from the study, significant additional concomitant drug treatment, or other therapy; and/or
- Test result is considered to be an AE by the investigator or sponsor.

Merely repeating an abnormal test, in the absence of any of the above conditions, does not constitute an AE. Any abnormal test result that is determined to be an error does not require reporting as an AE.

9.7. Serious Adverse Events

A serious adverse event is any untoward medical occurrence at any dose that:

- Results in death;

- Is life-threatening (immediate risk of death);
- Requires inpatient hospitalization or prolongation of existing hospitalization;
- Results in persistent or significant disability/incapacity (substantial disruption of the ability to conduct normal life functions);
- Results in congenital anomaly/birth defect.

Medical and scientific judgment is exercised in determining whether an event is an important medical event. An important medical event may not be immediately life-threatening and/or result in death or hospitalization. However, if it is determined that the event may jeopardize the subject or may require intervention to prevent one of the other AE outcomes, the important medical event should be reported as serious.

Examples of such events are intensive treatment in an emergency room or at home for allergic bronchospasm; blood dyscrasias or convulsions that do not result in hospitalization; or development of drug dependency or drug abuse.

9.7.1. Protocol-Specified Serious Adverse Events

There are no protocol-specified SAEs in this study. All SAEs will be reported by the investigator as described in previous sections and will be handled as SAEs in the safety database (see [Section 0 SAE Reporting Requirements](#)).

9.7.2. Potential Cases of Drug-Induced Liver Injury

Abnormal values in aspartate aminotransferase (AST) and/or alanine aminotransferase (ALT) levels concurrent with abnormal elevations in total bilirubin level that meet the criteria outlined below in the absence of other causes of liver injury are considered potential cases of drug-induced liver injury (potential Hy's law cases) and should always be considered important medical events.

The threshold of laboratory abnormalities for a potential case of drug-induced liver injury depends on the subject's individual baseline values and underlying conditions. Subjects who present with the following laboratory abnormalities should be evaluated further to definitively determine the etiology of the abnormal laboratory values:

- Subjects with AST or ALT and total bilirubin baseline values within the normal range who subsequently present with AST or ALT values ≥ 3 times the upper limit of normal (X ULN) concurrent with a total bilirubin value ≥ 2 X ULN with no evidence of hemolysis and an alkaline phosphatase value ≤ 2 X ULN or not available;
- For subjects with preexisting ALT **OR** AST **OR** total bilirubin values above the ULN, the following threshold values should be used in the definition mentioned above:
 - For subjects with preexisting AST or ALT baseline values above the normal range: AST or ALT values ≥ 2 times the baseline values and ≥ 3 X ULN, or ≥ 8 X ULN (whichever is smaller).

Concurrent with:

- For subjects with preexisting values of total bilirubin above the normal range:
Total bilirubin level increased from baseline by an amount of at least 1 X ULN **or**
if the value reaches ≥ 3 X ULN (whichever is smaller).

The subject should return to the investigational site and be evaluated as soon as possible, preferably within 48 hours from awareness of the abnormal results. This evaluation should include laboratory tests, detailed history, and physical assessment.

In addition to repeating measurements of AST and ALT, laboratory tests should include albumin, creatine kinase, total bilirubin, direct and indirect bilirubin, gamma-glutamyl transferase, prothrombin time (PT)/international normalized ratio (INR), and alkaline phosphatase. A detailed history, including relevant information, such as review of ethanol, acetaminophen, recreational drug and supplement consumption, family history, occupational exposure, sexual history, travel history, history of contact with a jaundiced person, surgery, blood transfusion, history of liver or allergic disease, and work exposure, should be collected. Further testing for acute hepatitis A, B, or C infection and liver imaging (eg, biliary tract) may be warranted. All cases confirmed on repeat testing as meeting the laboratory criteria defined above, with no other cause for liver function test (LFT) abnormalities identified at the time, should be considered potential Hy's law cases irrespective of availability of all the results of the investigations performed to determine etiology of the abnormal LFTs. Such potential Hy's law cases should be reported as SAEs.

